### **10.1.3 SAE reporting**

To ensure participant safety, every SAE, regardless of causality, occurring after the participant has provided informed consent and until 30 days following the last administration of cohort treatment must be reported to Novartis safety immediately, without undue delay, under no circumstances later than within 24 hours of learning of its occurrence. Detailed instructions regarding the submission process and requirements are to be found in the investigator folder provided to each site. Information about all SAEs is collected and recorded on the eSAE with paper backup Serious Adverse Event Report Form; all applicable sections of the form must be completed in order to provide a clinically thorough report.

All follow-up information for the SAE including information on complications, progression of the initial SAE and recurrent episodes must be reported as follow-up to the original episode within 24 hours of the investigator receiving the follow-up information. An SAE occurring at a different time interval or otherwise considered completely unrelated to a previously reported one must be reported separately as a new event.

If the SAE is not previously documented in the Investigator's Brochure or Package Insert (new occurrence) and is thought to be related to the study treatment, a CMO & PS Department associate may urgently require further information from the investigator for health authority reporting. Novartis may need to issue an Investigator Notification (IN) to inform all investigators involved in any study with the same study treatment that this SAE has been reported.

Suspected Unexpected Serious Adverse Reactions (SUSARs) will be collected and reported to the competent authorities and relevant ethics committees in accordance with [Detailed guidance on the collection, verification and presentation of adverse event/reaction reports arising from clinical trials on medicinal products for human use \('CT-3'\)](#) or as per national regulatory requirements in participating countries.

Any SAEs experienced after the 30 day period after the last cohort agent administration should only be reported to Novartis Safety if the investigator suspects a causal relationship to cohort treatment, unless otherwise specified by local law/regulations.

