### **9.3 Study stopping rules**

#### **Overall study stopping rules:**

If any of the following occur within a cohort, enrollment in the study within that cohort will be placed on hold, and no new participants may be dosed, however enrollment and dosing in any other concurrently running cohorts without safety concerns may continue.

- One or more study-treatment related SAEs
- Two or more similar SAEs, regardless of suspected drug-relatedness
- Two or more participants experience hypersensitivity reactions or injection reactions of moderate to severe intensity
- Two or more participants experience a similar AE, which was assessed as severe in intensity, and are considered as potentially related to the study treatment
- The Sponsor considers that the number and/or severity of AEs, abnormal safety monitoring tests or abnormal laboratory findings justify putting the study on hold

The study may resume following the safety review, if the Investigators and Sponsor agree it is safe to proceed.

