5. Action taken regarding with study treatment

All adverse events must be treated appropriately. Treatment may include one or more of the following:

- Dose not changed
- Drug interrupted/permanently discontinued

6. Its outcome

Conditions that were already present at the time of informed consent should be recorded in medical history of the participant.

Adverse events (including lab abnormalities that constitute AEs) should be described using a diagnosis whenever possible, rather than individual underlying signs and symptoms.

Adverse event monitoring should be continued for at least 30 days (or 5 half-lives or end of study visit, whichever is longer) following the last dose of study treatment.

Once an adverse event is detected, it must be followed until its resolution or until it is judged to be permanent (e.g., continuing at the end of the study), and assessment must be made at each visit (or more frequently, if necessary) of any changes in severity, the suspected relationship to the interventions required to treat it, and the outcome.

Information about adverse drug reactions for the investigational drug can be found in the Investigator's Brochure (IB).

Abnormal laboratory values or test results constitute adverse events only if they fulfill at least one of the following criteria:

- They induce clinical signs or symptoms
- They are considered clinically significant
- They require therapy

Clinically significant abnormal laboratory values or test results must be identified through a review of values outside of normal ranges/clinically notable ranges, significant changes from baseline or the previous visit, or values which are considered to be non-typical in participants with the underlying disease.

Instructions are outlined in the SOM for data capture methodology regarding AE collection for participants that fail screening.

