#### 17.1.1 Introduction

This treatment arm will evaluate canakinumab alone. As this treatment has an extended half-life, the EOC2 visit will serve as the end-of-study visit for participants randomized to this cohort.

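### In Cohort 1, SAEs after Day 171 that are judged unrelated lose 24-hour reporting for 110 of 140 post-dose days, so for them the any-causality hold trigger rests on data review with no stated timing

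*Protocol*

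**What the plan says.** **Reporting.** Protocol Section 10.1.3 sets one window for all agents. Every SAE, whatever its cause, "until 30 days following the last administration of cohort treatment must be reported to Novartis safety immediately", at most 24 hours after the site learns of it. An SAE occurring later "should only be reported to Novartis Safety if the investigator suspects a causal relationship to cohort treatment", with an exception where local law requires otherwise.

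**Hold rule.** Under Section 9.3, if a trigger is met, "enrollment in the study within that cohort will be placed on hold, and no new participants may be dosed". Two of the triggers are "One or more study-treatment related SAEs" and "Two or more similar SAEs, regardless of suspected drug-relatedness". The section gives neither an end date for counting events nor the data source from which they are counted.

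**Follow-up.** Section 10.1.1 uses a longer period for AEs: "Adverse event monitoring should be continued for at least 30 days (or 5 half-lives or end of study visit, whichever is longer". For Cohort 1, Section 17.1.1 states: "As this treatment has an extended half-life, the EOC2 visit will serve as the end-of-study visit". Section 4.5 justifies that visit by roughly five half-lives of safety observation and puts it 20 weeks after the last dose. SAP Section 2.1.1 runs the on-treatment period to EOC2 where that visit applies, and AEs starting in that period are summarised as treatment-emergent.

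**The concern.** For a long half-life agent the plan works with two different post-dose safety periods. AE monitoring, the EOC2 visit and the SAP summaries treat the time to Day 281 as a period of interest. The all-cause SAE reporting window stops at Day 171.

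The gap falls on one particular trigger. A single related SAE already puts the cohort on hold. What the any-causality trigger adds is therefore mainly clusters of SAEs that nobody has attributed to treatment, and these are the events that leave the 24-hour route after Day 171.

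Table 17-1 lists serious infection, including fatal sepsis and fatal pneumonia, among the agent's risks. Participants are aged 45 to 90 and investigators are blinded, so an investigator could judge an individual infection unrelated. A causality-blind cluster rule guards against that possibility. At stake is how quickly such a cluster would be recognised while other people in the cohort are still being enrolled or dosed.

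**Working it through.** **Inputs**
- Six doses every 4 weeks from Day 1 (Protocol 17.1).
- EOC1 on Day 171 and EOC2 on Day 281 (Section 3).
- Visit windows of ±2 days at Day 141 and Day 281 (Table 8-1).
- Half-life 26 days, five half-lives 130 days (Table 17-1); range 21 to 30 days (human pharmacokinetic data, Section 17.1.2.2.2).

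**1. The plan's own figure.** Last dose = 1 + 5 × 28 = Day 141. Time to EOC2 = 281 − 141 = 140 days = 20 weeks. This reproduces the 20 weeks in Section 4.5.

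**2. End of all-cause reporting.** 141 + 30 = Day 171, the same day as EOC1.

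**3. Length of the gap.** 281 − 171 = 110 days. As a share of post-dose follow-up, 110/140 = 0.786, or 79%.

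**4. Effect of visit windows.** Shortest: 279 − (143 + 30) = 106 days. Longest: 283 − (139 + 30) = 114 days.

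**5. Five half-lives instead of EOC2.** 141 + 130 = Day 271, and 271 − 171 = 100 days. Section 10.1.1 takes the longest of its options and EOC2 is later than Day 271, so 110 days is the applicable figure.

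**6. Exposure at 30 days.** Assuming simple first-order decay from the level after the last dose, the fraction left is 2^(−30/26) = 0.449. Over the stated range it is 2^(−30/21) = 0.371 to 2^(−30/30) = 0.50. This applies to the active arm only.

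**7. Routes to the sponsor, side by side**

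| SAE | To Day 171 | Day 171 to Day 281 |
|---|---|---|
| Suspected | 24 hours to safety unit | Still reported to safety unit |
| Not suspected | 24 hours to safety unit | CRF and clinical database only, unless local law requires more |

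**8. What the any-causality trigger adds.** If any SAE in a similar pair is held to be related, the related-SAE trigger has already fired. The any-causality trigger is decisive only when none is. If both occur after Day 171, neither has a 24-hour report. If one occurs before and one after, the second, which completes the pair, has none.

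**9. Timing of the remaining route.** Section 11.1 asks for timely CRF entry without giving a number of days. Section 10.3.1 leaves DMC meeting frequency to the charter and the Safety Surveillance Plan, which are not among these documents.

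**The case against.** A reader might infer that the any-causality trigger cannot work after Day 171. The documents do not support that. Section 9.3 does not say that events are counted from reports to the safety unit, and it sets no end date. Unsuspected SAEs are still collected to the end of the cohort (4.5, 10.1.1). Scheduled AE/SAE data go to the clinical database (Section 8), monitors verify SAE documentation (11.3), and a DMC reviews safety data (10.3.1). Section 9.3 also lets the sponsor call a hold on the number or severity of AEs. The rule can fire; what it loses is its prompt input.

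A reader might also infer a delay of up to 109 days, from an event on Day 172 that is first learned of on Day 281. That delay would come from visit spacing, not from the reporting rule. The 24-hour clock starts when the site learns of the event, a suspected SAE could be learned of just as late, and a longer reporting window adds no visit. Section 10.1.1 also allows for events volunteered between visits. The effect of Section 10.1.3 is narrower: once the site knows, the requirement is timely CRF entry instead of 24 hours.

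Three further points stand as limits:
- The documents give no rate at which investigators would call a serious infection unrelated. It is a listed risk, so they may well suspect the drug, and Table 17-1 describes the overall incidence as low.
- A hold stops only enrolment and new dosing in that cohort, so it has no effect once neither is under way.
- AE monitoring and expedited reporting serve different purposes, so different windows are not by themselves an error. Here the mismatch matters because a causality-blind trigger sits on top of a causality-filtered report.

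**Conclusion.** The point holds as a gap in prompt reporting. For a Cohort 1 participant who takes all six doses, SAEs not suspected to be drug-related lack 24-hour reporting for 110 of 140 post-dose days (79%; 106 to 114 days with visit windows), except where local law requires it. For those events the any-causality trigger depends on routine data entry and review whose timing these documents do not state.

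The figure assumes an agent with an EOC2 visit and a participant who completes dosing. Those who stop treatment early leave the study, with a visit 30 days after the last dose (9.1.1, Table 8-1). The length of any delay, and the overlap between early completers and later recruits, cannot be calculated because no entry deadline or accrual rate is given.

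The SAP (1.1) reports that the study was stopped after 34 of about 86 planned participants had been randomised, which limits the practical effect in Cohort 1. Section 10.1.3 nevertheless belongs to the core protocol, which Section 4.1 does not expect to change much, so the gap would carry over to any later agent with extended follow-up.

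**What to change.** In Section 10.1.3, align the all-cause 24-hour SAE reporting window with the follow-up already planned for the agent: 30 days after the last dose by default, and to EOC2 where that visit applies.

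Reconcile Sections 9.3, 10.1.1 and 10.1.3 so that they agree on the period and the data source feeding the existing hold triggers. The triggers are a matter for the sponsor and need not change for this purpose. If the reporting window is kept at 30 days, the protocol should at least say how, and how soon, later unsuspected SAEs are reviewed against Section 9.3.

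The cost is a short amendment and a modest number of additional SAE reports between Day 171 and Day 281. No visit or procedure is added. The change does not shorten the time until a site learns of an event; it shortens the time from then until the safety unit knows.

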#### **10.1.4 Pregnancy reporting**

##### **Pregnancies**

If a female trial participant becomes pregnant, the study treatment should be stopped, and the pregnancy consent form should be presented to the trial participant. The trial participant must be given adequate time to read, review and sign the pregnancy consent form. This consent form is necessary to allow the investigator to collect and report information regarding the pregnancy. To ensure participant safety, each pregnancy occurring after signing the informed consent must be reported to Novartis within 24 hours of learning of its occurrence. The pregnancy should be followed up to determine outcome, including spontaneous or voluntary termination, details of the birth, and the presence or absence of any birth defects, congenital abnormalities, or maternal and/or newborn complications.

Pregnancy should be recorded and reported by the investigator to the Novartis Chief Medical Office and Patient Safety (CMO&PS). Pregnancy follow-up should be recorded on the same form and should include an assessment of the possible relationship to the study treatment any pregnancy outcome. Any SAE experienced during pregnancy must be reported.

Depending on the investigational agent being tested, if a female partner of a male trial participant who took study treatment in this study becomes pregnant, pregnancy outcomes should be collected. Consent to report information regarding these pregnancy outcomes should be obtained from the mother.

After consent is provided, the pregnancy reporting will occur up to one year after the estimated date of delivery.

Please see [Section 17](#) for further guidance on each agent, if applicable, including whether male contraception is required for the agent.

### 10.1.5 Reporting of study treatment errors including misuse/abuse

Medication errors are unintentional errors in the prescribing, dispensing, administration or monitoring of a medicine while under the control of a healthcare professional, participant or consumer (EMA definition).

Misuse refers to situations where the medicinal product is intentionally and inappropriately used not in accordance with the protocol.

Abuse corresponds to the persistent or sporadic, intentional excessive use of a medicinal product, which is accompanied by harmful physical or psychological effects.

Study treatment errors and uses outside of what is foreseen in the protocol will be recorded on the appropriate CRF irrespective of whether or not associated with an AE/SAE and reported to Safety only if associated with an SAE. Misuse or abuse will be collected and reported in the safety database irrespective of it being associated with an AE/SAE within 24 hours of Investigator's awareness.

**Table 10-1      Guidance for capturing the study treatment errors including misuse/abuse**

Treatment error type	Document in Dosing CRF (Yes/No)	Document in AE eCRF	Complete SAE form
Unintentional study treatment error	Yes	Only if associated with an AE	Only if associated with an SAE
Misuse/Abuse	Yes	Yes	Yes, even if not associated with a SAE

For more information on AE and SAE definition and reporting requirements, please see the respective sections ([Section 10.1.1](#) and [Section 10.1.2](#), respectively).

## 10.2 Additional Safety Monitoring

### 10.2.1 Liver safety monitoring

To ensure participant safety and enhance reliability in determining the hepatotoxic potential of an investigational drug, a standardized process for identification, monitoring and evaluation of liver events has to be followed.

Please refer to [Table 16-1](#) in [Section 16](#) for complete definitions of liver laboratory triggers and liver events.

Once a participant is exposed to study treatment, every liver event defined in [Table 16-1](#) should be followed up by the investigator or designated personnel at the trial site, as summarized below. Additional details on actions required in case of liver events are outlined in [Table 16-2](#). Repeat liver chemistry tests (i.e., ALT, AST, TBL, PT/INR, ALP and G-GT) to confirm elevation.

- These liver chemistry repeats will be performed using the central laboratory. If results will not be available from the central laboratory, then the repeats can also be performed at a local laboratory to monitor the safety of the participant. If a liver event is subsequently

reported, any local liver chemistry tests previously conducted that are associated with this event should have results recorded on the appropriate CRF.

- If the initial elevation is confirmed, close observation of the participant will be initiated, including consideration of treatment interruption if deemed appropriate.
- Discontinuation of the investigational drug (see Discontinuation of Study Treatment [Section 9.1.1](#)), if appropriate
- Hospitalization of the participant if appropriate
- Causality assessment of the liver event
- Thorough follow-up of the liver event should include:
  - Repeating liver chemistry tests two or three times weekly. Testing should include ALT, AST, ALP, PT/INR, and GGT. If total bilirubin is elevated  $> 2 \times$  ULN, fractionation into direct and indirect bilirubin is required. To rule out muscular origin or transaminase elevations, CPK should be measured along with liver chemistry tests. Frequency of retesting can decrease to once a week or less if abnormalities stabilize or the study drug has been discontinued and the participant is asymptomatic. Retesting should be continued up to resolution.
  - Obtaining a more detailed history of symptoms and prior or concurrent diseases.
  - Obtaining a history of concomitant drug use (including non-prescription medications and herbal and dietary supplement preparations), alcohol use, recreational drug use, and special diets.
  - Exclusion of underlying liver disease, as specified in [Table 16-4](#)
  - Imaging such as abdominal US, CT or MRI, as appropriate.
  - Obtaining a history of exposure to environmental chemical agents.
  - Considering gastroenterology or hepatology consultations

All follow-up information and procedures performed must be recorded as appropriate in the CRF.

Additional details can be found in the 'Liver Event Guide and Checklist' guidance document in the Appendix of the SOM, which details how the various assessments and results should be recorded, and other details that should be ascertained from the participant.

### **10.2.2 Renal safety monitoring**

Once a participant is exposed to study treatment, the following two categories of abnormal renal laboratory alert values should be assessed during the study period:

- Serum creatinine increase  $\geq 25\%$  compared to baseline during normal hydration status
- Any one of the following:
  - Urine protein-creatinine ratio (PCR)  $\geq 1\text{g/g}$  or  $\geq 100\text{ mg/mmol}$ , OR
  - New onset dipstick proteinuria  $\geq 3+$ , OR
  - New onset dipstick hematuria  $\geq 3+$  (after excluding menstruation, UTI, extreme exercise, or trauma)

Abnormal renal event findings must be confirmed within 24-48 hours after the first assessment.

Once a participant is exposed to study treatment, renal laboratory alerts or renal safety events should be monitored and followed up by the investigator or designated trial staff as summarized in [Section 16.3](#).

Every renal laboratory trigger or renal event should be followed up by the investigator or designated personnel at the trial site as summarized in [Section 16.3](#).

Additional details can be found in the ‘Renal Event Guide and Checklist’ guidance document in the Appendix of the SOM, which details how the various assessments and results should be recorded, and other details that should be ascertained from the participant.

### **10.2.3 Prospective suicidality assessment**

The Columbia-Suicide Severity Rating Scale (C-SSRS) is a questionnaire that prospectively assesses suicidal ideation and suicidal behavior. The C-SSRS must be administered at each visit, including unplanned visits.

The C-SSRS will be administered by an individual who has received training and certification in its administration. At the first study visit, the “baseline/screening” version of the C-SSRS will be administered. This version assesses suicidal ideation and suicidal behavior during the participant’s lifetime and during a predefined period. At subsequent visits, the “since last visit” version will be administered.

A validated version of the C-SSRS will be used to capture self-reported C-SSRS data utilizing an electronic tablet format (eC-SSRS). The eC-SSRS uses a detailed branched logic algorithm to perform the C-SSRS participant interview, evaluating each participant’s suicidality ideation and behavior in a consistent manner. If the alert system assesses the participant as having positive suicidal signs, the investigator will be immediately notified by either email, and/or via telephone.

If, at any time after screening and/or baseline, the score is “yes” on item 4 or item 5 of the suicidal ideation section of the C-SSRS or “yes” on any item of the suicidal behavior section, the participant must be referred to a mental health care professional for further assessment and/or treatment. The decision on whether the study treatment should be discontinued is to be taken by the investigator in consultation with the mental health professional to whom the participant is referred.

In addition, all life-threatening events must be reported as SAEs. For example, if a participant answers “yes” to one of the questions in the suicidal behavior section, an SAE must be reported if the event was life-threatening. All events of “Non-Suicidal Self-Injurious Behavior” (question also included in the suicidal behavior section) should be reported as AEs and assigned the appropriate severity grade.

## **10.3 Committees**

### **10.3.1 Data Monitoring Committee**

As described in the [FDA Draft Guidance for Industry: Safety Assessment for IND Safety Reporting \(CDER 2015\)](#), this study will include an external Data Monitoring Committee (DMC). The DMC will function independently of site investigators participating in the study. The DMC will assess the progress of the EXPLAIN-AD treatment cohorts and the safety

data. The Sponsor will continue, modify or terminate investigational agents based on these reviews.

Specific details regarding composition, responsibilities, data monitoring, meeting frequency, and documentation of DMC reports, minutes, and recommendations are described in the Safety Surveillance Plan for each agent and the DMC Charter.

